It is possible to identify further patient subgroups, but we have prioritised a set of seven key contrasts. Interpretation becomes more problematic whenever more subgroups are specified, and our statistical procedures are at greater risk of finding spurious 'significant' differences in impact purely by random chance due to multiple testing across many hypotheses using the same data set. This risk of multiple testing will be addressed by Dunn-Sidak corrections to hypothesis tests (as a more precise alternative to Bonferroni adjustment). We will report both the Dunn-Sidak corrected and uncorrected p-values arising from hypotheses tests of outcome modelling across the pooled sample and the pre-specified subgroups.

All below analyses will be undertaken as stratified subgroups, but will only be reported where there is a minimum sample size across the three evaluations of 50 MDT-treated patients and 250 potential control individuals, ie where statistical estimates are expected to be stable and reliable.

We will construct the counterfactual for the MDT-treated patients in each subgroup separately (unless otherwise specified below) using entropy balancing or inverse probability of treatment weighting (IPTW), used as appropriate.

- 1. **By social context:** based on the exploratory analyses for incorporating address-level data, we will determine the most useful subgroup based on the social context variables identified (eg living alone).

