The IPAEOPGP is a risk prediction model of hospital admissions that builds on and improves on earlier models such as the PARR algorithm and identifies a number of comorbidities predictive of hospital admission.^{68,69} Selected variables from IPAEOPGP identifiable in inpatient hospital records and not captured in the Elixhauser list were included in the list of potential baseline variables.

After this **stacked** data set is generated across MDT-treated units and control units originally selected within each study by genetic matching, we will run standard quality checks for completeness and plausibility across the sample, in order to avoid the inclusion of erroneous data. In certain cases, we may address missing data by appropriate multiple imputation or complete case analysis.

We will **divide the data set into the pre-specified subgroups detailed above** and check the sample sizes. Where **the pre-specified subgroups are too small** (ie fewer than 50 intervention patients across the stacked data), no further analyses on that subgroup will be done. This is because small sample sizes will compromise our ability to generate reliable and stable estimates of the impact of MDTs and there will be lower power to detect effects.

If, however, the pre-specified subgroups are large enough (at least n=50 interventions, and at least n=250 potential controls in the donor pool for weighting), we will address the subgroup analysis through creating new counterfactuals for each subgroup by reweighting using entropy balancing methodology as detailed above.

Exploratory data analyses: improving on unobserved confounding by exploring social context factors and a proxy for end of life

By using pseudonymised address information for all individuals registered with a GP from the NHAIS data and linking this to SUS, we will investigate the relevance of a number of variables relating to social context, which may be be proxies for social isolation, instability or other factors that may affect an individual's risk of emergency hospital use and may be a referral criterion for MDTs.

We will identify and explore a number of indicators:

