We will initially identify subgroup effects based on the statistical significance and absolute magnitude of their coefficients during outcome regression. Where these terms are significant, we may carry out further post hoc stratified analysis by repeating the weighting algorithm for MDT patients in this subgroup only, in order to generate conditional effect estimates that may be of particular interest to policymakers in planning future targeted MDT implementation. In other words, we may run the entropy balancing algorithm up to seven times to obtain an appropriate counterfactual for each of the patient subgroups of interest. Combined with the reweighting of the overall MDT pool and each of the MDTs, this implies up to 15 sets of entropy balancing and/or IPTW results.

However, we will drop subgroup analyses where there appears to be poor 'overlap' of key characteristics such as age or gender distribution between the MDT patients and the reweighted controls. This is because such exchangeability between intervention and counterfactual populations is a prerequisite for the validity of treatment effect estimates.^{62,72}

For example, it will not be valid or useful to compare hospital activity among a population of MDT patients with dementia who are primarily female and over 70 with a population of control patients who are primarily male and under 50. Where exchangeability is poor, entropy balancing typically fails to converge due to data sparsity. PS or IPTW may converge but results should be interpreted cautiously due to the risk of model misspecification and biased estimates. As poor overlap signals missing data observations that would otherwise have to be entirely extrapolated, no statistical method can address this flaw if it arises.

In the event of non-significant regression coefficients, small sample sizes, poor intervention-counterfactual overlap, or other issues we may uncover during the exploratory analyses that constrain statistical feasibility, we will only carry out and report a smaller set of regression-adjusted subgroup analyses – where we are confident the results are meaningful and reliable (ie overlap appears to be satisfied and statistical models including many covariates are successfully fitted). We anticipate that some of the subgroups will most likely fail one or more of these conditions.

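### The SAP promises a reweighted analysis of every large enough pre-specified subgroup, then allows statistical significance to decide which are reweighted and reported, and never states the Dunn-Sidak number of tests

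*SAP*

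**What the plan says.** **Methods, Patient subgroups.** The SAP says "we have prioritised a set of seven key contrasts". The stated gate is size only: "All below analyses will be undertaken as stratified subgroups, but will only be reported where there is a minimum sample size" (50 treated patients and 250 potential controls). On the counterfactual it says "We will construct the counterfactual for the MDT-treated patients in each subgroup separately (unless otherwise specified below").

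**Exploratory data analyses on heterogeneity.** The same size rule is repeated. For subgroups that meet it, "we will address the subgroup analysis through creating new counterfactuals for each subgroup by reweighting using entropy balancing methodology".

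**Main analysis, Pooled and subgroup analyses.** A different rule appears: "We will initially identify subgroup effects based on the statistical significance and absolute magnitude of their coefficients during outcome regression". Then: "Where these terms are significant, we may carry out further post hoc stratified analysis by repeating the weighting algorithm for MDT patients in this subgroup". A later paragraph opens with "In the event of non-significant regression coefficients, small sample sizes, poor intervention-counterfactual overlap" and concludes that "we will only carry out and report a smaller set of regression-adjusted subgroup analyses".

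**Multiplicity (Patient subgroups).** Dunn-Sidak is named, and corrected and uncorrected p-values are promised across the pooled sample and the pre-specified subgroups. No number of tests is given. The SAP does not say which p-value drives the screen, or at what level.

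**The concern.** Two analysts could each follow this SAP faithfully and report different subgroups. One would reweight and report every subgroup that meets 50/250. The other would run a regression first, reweight only what came out significant, and leave out the rest.

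The second route selects on the results it then presents. Research question 3 asks which patients see a reduction or an increase in unplanned hospital use, and the SAP describes finding such heterogeneity as the main value of pooling. A well-estimated null is an answer to that question, and the screen allows it to go unreported. Estimates kept because they were significant are too large on average.

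The screen also comes before the subgroup has its own weights. The SAP itself warns, about the original matching, that balance over the whole sample is not balance within subgroups. A subgroup that fails the screen may therefore never receive the counterfactual promised elsewhere.

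Finally, a Dunn-Sidak correction has no defined level until the number of tests is stated, and that number should not depend on how many subgroups survive a screen.

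**Working it through.** **1. The SAP's own count.** One pooled contrast, three by MDT and four by MDT and CCG give 1 + 3 + 4 = 8. Adding seven subgroups gives 8 + 7 = 15, which matches the stated maximum of 15 sets of weighting results. All seven subgroup runs are thus already allowed for.

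**2. The two rules side by side.**

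| Step | Patient subgroups; exploratory section | Pooled and subgroup analyses |
|---|---|---|
| Which subgroups are reweighted | All that meet 50/250 | Those with significant terms, and then only optionally |
| Status of the stratified analysis | Pre-specified | Called post hoc |
| Grounds for not reporting | Too few patients | Also non-significance, poor overlap, other feasibility problems |

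Size, overlap and model convergence can be judged without looking at the effect estimate. Significance cannot.

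**3. Exaggeration after selection.** Assume a two-sided 5% screen and an estimate in standard-error units distributed N(δ, 1), with δ = 1.96 + z(power). Ignoring the small opposite tail, the mean of retained estimates divided by the truth is

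R = 1 + φ(δ − 1.96) / (power × δ).

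- 50% power: δ = 1.96, φ(0) = 0.399. R = 1 + 0.399/(0.5 × 1.96) = 1.41.
- 80% power: δ = 2.80, φ(0.84) = 0.280. R = 1 + 0.280/(0.8 × 2.80) = 1.12.
- 20% power: δ = 1.12. R = 1 + 0.280/(0.2 × 1.12) = 2.25. Simulation with both tails gives 2.23.

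The reported figure would be the reweighted estimate, not the screening one. If the two have correlation ρ and equal precision, the factor is 1 + ρ(R − 1). At ρ = 0.5 (assumed) it is about 1.6, 1.2 and 1.06 at 20%, 50% and 80% power.

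**4. Multiplicity.** Inputs are seven subgroups (Patient subgroups) and five primary outcomes (Study endpoints), so 7 × 5 = 35 tests.

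- Uncorrected at 5%: 35 × 0.05 = 1.75 false positives expected if no true differences exist. The chance of at least one under independence is 1 − 0.95^35 = 0.83. For seven tests it is 1 − 0.95^7 = 0.30.
- Dunn-Sidak per-test level: 1 − 0.95^(1/k).

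| Reading of the family | k | Per-test level |
|---|---|---|
| Subgroups only | 7 | 0.0073 |
| Subgroups × outcomes | 35 | 0.00146 |
| The 35, plus the overall pooled test on each of five outcomes | 40 | 0.00128 |
| All 15 weighting sets × outcomes | 75 | 0.00068 |

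These readings span about an 11-fold range (0.0073/0.00068).

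- If k were set to the number of tests passing an uncorrected 5% screen, simulation under independence gives a family-wise error of about 29% with 7 tests and 69% with 35.

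**The case against.** The strongest reply is that the main-analysis text is permissive. It says stratified analysis may follow. It describes the smaller reported set in terms of satisfied overlap and successful model fitting, not p-values. Patient subgroups also promises p-values across the pre-specified subgroups. A reader might infer that the SAP plans to report only significant subgroups, and the text does not support that. What stands is that non-significance is listed as a trigger for cutting the set, and nothing reconciles this with the size-only rule.

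A reader might also infer that the multiplicity family leaves out the five primary outcomes. The SAP does not say so, and its wording about tests of outcome modelling could include them. The supportable point is that k is missing.

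A third tempting reading is that the screened coefficients are subgroup main effects, which are prognostic and do not show effect modification. The SAP does not name the term. However, the Objectives speak of assessing whether the intervention effect differs between end-of-life subgroups, so interactions are probably meant. This needs clarifying and is not proof of a wrong test.

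On size, independence overstates the family-wise figures. Chronic ACS and UCS admissions are types of emergency admission, and the frailty markers include dementia through cognitive impairment. Multimorbidity and frailty may be large subgroups among 5,411 patients, with little exaggeration. All of this is fair, and it is why the figures are given as a range and an upper end.

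The addendum route does not resolve the conflict. It covers exploratory decisions, whereas this screen is written into the main analysis.

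**Conclusion.** The contradiction is plain in the current text and needs no assumption. As written, the main-analysis section permits, but does not require, results-based selection of the subgroups that answer research question 3.

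The size of the harm is conditional. With selection at p<0.05, exaggeration is about 2.2 times at 20% power, 1.4 times at 50% and 1.1 times at 80%, and smaller where the reweighted estimate departs from the screening one. Neither the alpha nor any subgroup power is in the SAP. The 83% chance of at least one false signal is an upper-end figure for 35 independent, uncorrected tests with no true differences. Separately, the Dunn-Sidak correction cannot be applied reproducibly until k is stated.

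**What to change.** In Pooled and subgroup analyses:

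- Delete the screen on significance and magnitude, and delete non-significant coefficients as a ground for not carrying out or reporting an analysis.
- Keep the size, overlap and convergence rules. Keep the separate end-of-life procedure under Patient subgroups, because that status is defined by death within 90 days after enrolment and should not be forced into a common template.
- For every subgroup that meets those rules, report the MDT-by-subgroup interaction with its confidence interval and the reweighted subgroup ATT, whatever the p-value.

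In Patient subgroups, state the Dunn-Sidak k in advance, counting subgroups, primary outcomes and the pooled-sample tests that the section already includes. As examples, the 35 subgroup interactions alone give 0.00146 per test, and adding five overall pooled tests gives k = 40 and 0.00128. The choice is the authors', but k should stay fixed if subgroups are later dropped.

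The cost is wording, plus those of the seven already budgeted weighting runs that the screen would have skipped. The SAP puts entropy balancing at minutes rather than weeks. The downside is a stricter corrected threshold.

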We will do some initial exploratory analyses to inform some of the final design decisions, as detailed in this SAP. These will be documented in an addendum to the SAP before starting the main analyses.

Reweighting of the pooled sample to build a new counterfactual using entropy balancing

Directly combining the three original analysis data sets to specify subgroups is expected to result in some imbalance in the MDT and matched control groups, due to differences in characterstics used to select the counterfactuals (in particular, the use of risk scores in these ECS and EPC programmes and their evaluations, but not in NEHF). Original matching procedures were also not optimised for subgroup balance, but rather balance across the whole population sample. This would therefore introduce bias to the statistical estimates in crude post hoc analysis.

The previous method used for robustly generating the counterfactual in the IAU evaluations of MDTs – genetic matching (based on the generalised Mahalanobis distance²²) – is attractive for reducing bias. It applies relatively loose parametric assumptions extending from the principles of propensity score matching to offer a principled, replicable approach to identifying the most similar control units from high-dimension, large samples of data. However, genetic matching is very computationally intensive and would require unwieldy calculation time for the pooled analysis.

An alternative algorithm to create a counterfactual, entropy balancing⁶² is much quicker and more efficient than genetic matching, computing in a matter of minutes rather than weeks or months. This is because entropy balancing reweights all available control units to be similar to the treated sample, rather than selecting individually matched units to map to each intervention unit, which excludes many potential control units that fail to minimise the distance metric of interest. As such, it is less straightforward to interpret, but it generates an equally robust counterfactual in order to estimate treatment impacts. The Health Foundation data analytics team has previously used entropy balancing and found consistent results with genetic matching in evaluation of integrated care pathways inTower Hamlets.⁶³ Other empirical literature using entropy balancing in health policy and economics has been widely demonstrated and accepted.^{64,65}

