In NEHF, potential controls (consisting of individuals registered with a GP in NEHF) were only defined by age across the study sample, irrespective of locality (the equivalent to Fylde neighbourhoods). Thus, the youngest control individual retained for analysis was at most 2 years younger than the youngest overall NEHF patient (irrespective of gender), with this rule applied symmetrically for maximum ages.

For the planned analyses, the criteria for 'slimming' potential donor controls by age has been adapted for consistency across the three studies: control pools are pre-specified to be 2 years around the minimum and maximum ages of all MDT intervention patients, by gender, in the respective MDT studies.

Exploratory data analyses on heterogeneity, on stacked original analysis data (using matched controls)

First, we will 'stack' or directly combine the three original matched data sets, according to a commonly mapped variable list that has been pre-defined (Table 5). Variable names and definitions are largely but not entirely consistent between the three IAU evaluations. Some will be adjusted so that both our stacked matched data set and our pooled data set have consistent definitions, variables and outcomes across all three studies. For example, for Fylde we will calculate emergency admission-associated length of stay, while the original analysis looked at emergency hospital bed days. Similarly, some of the flags used for risk adjustment will change, including removing some historic hospital activity and updated definitions for mental ill health flags in Fylde (see Table 5). In this initial phase, the individual intervention and matched control patients, as well as follow-up period, will be exactly the same units as those included in the original evaluations.

We will also add a set of new variables that capture social context characteristics, which aim to improve the similarity between the intervention group and their counterfactual. These are discussed in the next section.

Table 5. Potential baseline variables for regression on stacked data sets and for entropy balancing on pooled data

| V | ariables at patient level | Changes to the original individual study analyses | | | | | | | | | | | | | | | | | | | | | | | | | | | | | | | | |
|--------|---|---|--|---|--|--|---|---|--|---|---|--|--|---|---|---|---|--|---|--|---|--|---|---|---|--|---|---|---|---|--|--|---|--|

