As in the original studies, we will **estimate outcomes** based on four sets of covariates: all 'base' covariates (as described in Table 5); a smaller set of 'core' covariates that exclude historic hospital activity; covariates selected from data-driven lasso regression; and unadjusted or crude results. The lasso is a variation of ridge regression that applies a machine learning algorithm to principled variable selection – additional terms are penalised such that included variables achieve an optimal and replicable signal-to-noise ratio and improves upon the ad hoc nature of previously conventional procedures such as stepwise selection.²³ The final model will always be adjusted for covariate unless the algorithm entirely failed to converge due to sparse data. The most appropriate generalised linear model, selected from several pre-specified distributions, and covariate list will be chosen based on the Akaike Information Criterion²⁴ and other diagnostics, such as comparing observed vs predicted zeros (for count variables), and root mean squared errors (RMSE). Depending on the outcome being modelled, the likelihood distributions used are typically Poisson or inverse negative binomial (for count outcomes) – potentially with some corrections for zero-values inflation or over-dispersion – or logistic (for binary outcomes).

For the overall pooled data set, we will generate generic **forest plots** per conventional meta-analytic summaries that depict the weighted ATT estimates from across the three evaluations, and also compare the results from fixed-effect vs random-effect models (where the latter will be more valid if the study samples contribute 'true' heterogeneity). The results of

the model fitting may also be reported as tabular effect estimates and 95% confidence intervals. We will also calculate and report commonly accepted measures for study heterogeneity in the meta-analysis, namely the *H* and *I*² statistics⁷³ as well as τ^{274} . We will also report the difference in effect estimates by fixed and random effects for the MDT treatment.

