To check for outliers in the pooled sample and subgroup samples that may skew or overly bias our estimates, we will use standard visual plots such as covariate plots and quantile-quantile ('Q-Q' plots) to inspect for unexpected or problematic patterns in regression results. Although we do not anticipate this to be an issue as we do not apply simple linear regression in any cases, we may resolve problematic covariate-outcome patterns using standard transformations (eg higher-order terms, log variables). For entropy balancing/ PSM/IPTW, we will apply further matching diagnostics of balance (eg standardised mean difference plots or SMDs, Kolmogorov-Smirnov test (KS), pseudo-propensity score plots (PPS), variance ratio tests (VRT)). Residual imbalances above a 10% SMD will be noted, and where they show systematic and large bias, we may drop the corresponding subgroup analysis. With the entropy balancing algorithm, SMDs are typically optimised to zero across (nearly) all covariates as an inherent property of the algorithm, and merely signal that the mathematical model has successfully calculated. Thus, other diagnostics such as PPS plots are important to check that the entropy balancing algorithm is not invalid, eg due to extreme weights applied to a very small number of control units relative to the intervention group. For the exact statistical tests (KS, VRT), we pre-specify a failure threshold of p<0.05. In all cases, we will report our diagnostics in technical appendices to the main outcome report, particularly where judgement involves visual inspection.

Conventional pooled analyses on the 'stacked' matched data set – in case no valid alternative to genetic matching is found within the constraints of the timelines

If we do not find a valid alternative to genetic matching within the timelines set, we may use the stacked matched data set to generate crude outcome comparisons between MDT users and their matched controls, overall, for each study and for all subgroups.

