For all analyses and finalised list of subgroup analyses, we will apply conventional meta-analysis techniques based on assumed homogeneity of effects. We would then generate **estimated treatment effect estimates across all three MDTs**. The effect estimates from the three studies should be more numerically **precise** due to the larger sample size available from pooling, and based on the previous ATTs we can already anticipate that for the overall study pool these will show an approximately 30% to 40% increase in the primary study outcomes (A&E attendances and emergency admissions).

We will generate forest plots depicting the outcomes from the 'stacked' data set, and also compare the results from fixed-effect vs random-effect models (where the latter will be more valid if the study samples contribute 'true' heterogeneity) as described above, but anticipate that this crude estimate will be less precise than the reweighted estimates described above.

Relatively poor balance from SMD plots or other exploratory diagnostics may suggest that a conventional approach to pooled analysis using the original combined data set is biased or invalid, for one or many of the results sets. Even if SMD plots and other diagnostics do not suggest imbalance, homogeneity of effects is a quite strong causal assumption that has been critiqued elsewhere.⁷⁶The effect estimates from conventional meta-analysis across a small sample of n=3 studies would therefore be relatively weak evidence regardless of ultimate effect estimates, and suggest hypotheses for further validation.

For this reason, we strongly prefer effect estimates generated from entropy balancing and appropriate reconstruction of counterfactuals across the sample of interest, as they provide much stronger evidence for causal inference about the impact of MDTs.

Patient and Public Involvement and Engagement (PPIE)

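### The optional fallback on the stacked matched data is described as crude, including for all subgroups, which conflicts with the plan's covariate-adjustment rules and its own warning of bias

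*SAP*

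**What the plan says.** The fallback is in the section *Conventional pooled analyses on the 'stacked' matched data set*. When no valid alternative to genetic matching is found within the timelines, the team may "generate crude outcome comparisons between MDT users and their matched controls, overall, for each study and for all subgroups". The same section later says they "anticipate that this crude estimate will be less precise than the reweighted estimates described above".

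Other parts of the SAP bear on how that analysis should be done:

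- *Pooled and subgroup analyses* lists four covariate sets for outcome modelling. The last two are "covariates selected from data-driven lasso regression; and unadjusted or crude results". It then states: "The final model will always be adjusted for covariate unless the algorithm entirely failed to converge due to sparse data".
- The same section says that where feasibility is constrained (non-significant coefficients, small samples, poor overlap or other problems), "we will only carry out and report a smaller set of regression-adjusted subgroup analyses".
- *Reweighting of the pooled sample* says: "Directly combining the three original analysis data sets to specify subgroups is expected to result in some imbalance". It notes that the original matching was not optimised for subgroup balance, and concludes: "This would therefore introduce bias to the statistical estimates in crude post hoc analysis".
- Table 5 is titled "Potential baseline variables for regression on stacked data sets and for entropy balancing on pooled data", so a covariate list for regression on these data already exists.

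**The concern.** The fallback names an unadjusted estimator for exactly the comparisons in which the plan expects imbalance. Within a subgroup cut from the stacked data, MDT patients and controls need not be balanced on prior hospital use or comorbidity. An apparent subgroup effect, or a difference between subgroups, could then be residual imbalance. The plan gives subgroup heterogeneity as the main value of pooling, so this affects the results readers will look at first.

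The text also leaves the estimator open. An analyst who follows the fallback section reports crude figures, and one who follows the general modelling rule reports adjusted ones. The choice would be made after entropy balancing results had been seen. That is at odds with the stated aim of the SAP, that design and method choices should not be influenced by the data.

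**Working it through.** **1. What crude means here.** The list of four covariate sets pairs crude with unadjusted. This is the only place where the SAP explains the word, so the natural reading of the fallback is an unadjusted comparison.

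**2. The statements side by side.**

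- Estimator: crude in the fallback section; adjusted under the general rule, whose only exception is complete non-convergence with sparse data. Lack of time is not that exception.
- Subgroups: crude and for all of them in the fallback section; only a smaller, regression-adjusted set under the feasibility rule.
- Subgroup size: all of them in the fallback section; no further analysis below 50 intervention patients under the stacked-data exploratory section. Subgroups with poor overlap are also to be dropped. The fallback section itself goes on to mention a finalised subgroup list.
- Validity: the fallback section expects the crude estimate to be less precise, whereas the reweighting section says such an analysis is biased. The fallback section adds later that the conventional approach may prove biased or invalid.

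**3. The plan's own anticipated result.** The fallback section expects an increase of roughly 30% to 40% in A&E attendances and emergency admissions, based on the previous effects. I pooled the Table 4 rate ratios by inverse variance, with SE = (ln upper − ln lower) / (2 × 1.96).

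- A&E attendances: 1.26 (1.15–1.38), 1.40 (1.28–1.52), 1.33 (1.16–1.54). The SEs are 0.047, 0.044 and 0.072. Fixed effect 1.33 (1.26–1.41), random effects 1.33 (1.24–1.43), I² 26%.
- Emergency admissions: 1.27 (1.15–1.41), 1.42 (1.29–1.56), 1.43 (1.23–1.67). The SEs are 0.052, 0.048 and 0.078. Fixed effect 1.36 (1.28–1.45), random effects 1.36 (1.26–1.48), I² 32%.

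The stated range is reproduced. *Original study results* says the Table 4 effects are regression-adjusted, so the figure attached to a crude analysis is an adjusted one.

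**4. Where the harm would lie.** The initial stacked data set keeps exactly the patients and matched controls of the original evaluations, and the matching was optimised for each whole sample. Adjusted per-study effects for A&E attendances, emergency admissions, and chronic ACS and UCS admissions are in Table 4, and step 3 shows that a pooled adjusted effect follows from them. Subgroups have no such adjusted result to fall back on.

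**5. Size.** The SAP gives no crude rates and no subgroup balance, so the bias cannot be computed. The following is an illustration on assumed inputs only. Bias = exp(SMD × SD × ln r) − 1, where SD is that of prior-year emergency admissions (assumed 1.5 to 2) and r is the outcome rate ratio per prior admission (assumed 1.10 to 1.30, so ln r is 0.095 to 0.262).

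- SMD 0.1 (the plan's flag for residual imbalance): exponent 0.1 × 1.5 × 0.095 = 0.014 to 0.1 × 2 × 0.262 = 0.052, a bias of 1.4% to 5.4%.
- SMD 0.2 (assumed): exponent 0.029 to 0.105, a bias of 2.9% to 11.1%.

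For a subgroup of one-tenth of the sample (assumed), the SE for A&E attendances is about 0.029 × √10 = 0.092, where 0.029 is the pooled SE from step 3. The illustrative bias is then about 0.014/0.092 = 0.2 to 0.105/0.092 = 1.1 standard errors.

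**The case against.** The best case for the plan has four parts.

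- **The fallback is remote and optional.** *Comparison of matching alternatives in the pooled data set* requires that entropy balancing be inconsistent and also that time not allow other methods to be explored. IPTW and propensity score matching come first, and the reliability of the stacked analyses is then considered. Both sections say may. This stands. A reader might infer that missing the consistency threshold alone leads to crude reporting, but the text does not say that.
- **The weakness is disclosed.** The fallback section calls the evidence relatively weak, suitable for suggesting hypotheses, and strongly prefers entropy balancing. This stands too. Disclosure limits the harm, but it does not justify leaving out an adjustment that is already specified.
- **The contradiction is not with a rule written for the fallback.** The adjustment rule is a general one and does not name this analysis. It also lists crude results among the routine outputs, so showing crude figures is no breach in itself. The Table 5 title belongs to exploratory work and does not define the fallback estimator. All this is correct. A reader might infer that the SAP somewhere declares the fallback always adjusted, and it does not.
- **Crude could mean not reweighted.** The contrast with the reweighted estimates and the adjusted 30% to 40% both allow that reading. It is possible, but it goes against the SAP's own pairing of crude with unadjusted. If it was intended, a sentence should say so.

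**Conclusion.** The point holds as a conflict in the specification of an optional, last-resort analysis. Read in the SAP's own terms, the fallback reports unadjusted comparisons for all subgroups. That departs from the general adjustment rule and from the restriction to regression-adjusted subgroup analyses, and the plan itself calls such comparisons biased.

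The consequence is mainly confined to subgroups, and its size is not known. A reader might divide an assumed imbalance by the whole-sample standard error of about 0.03 and infer a bias of several standard errors in the overall result. The documents do not support that: the original matching was optimised for each whole sample, and the SAP's bias statement concerns stacking in order to form subgroups. A reader might also infer that crude fallback results would be judged against Table 4. The SAP uses Table 4 to validate entropy balancing and to anticipate the fallback result, but sets no such test for the fallback.

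The conclusion rests on the wording alone. It does not depend on the illustrative figures.

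**What to change.** In *Conventional pooled analyses on the 'stacked' matched data set*:

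- State that the reported estimate on the stacked data, particularly for subgroups, is the regression-adjusted model from *Pooled and subgroup analyses*, with Table 5 covariates.
- Show crude figures only alongside the adjusted ones, labelled as unadjusted.
- Replace the reference to all subgroups with those that pass the existing rules: at least 50 intervention patients, and adequate overlap, assessed here against the matched controls because there are no reweighted ones.

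The models, covariates and subgroup rules already exist, so the cost is a change of wording and slightly more analysis work.
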